8.2.4. Non-Parametric Analyses

8.2.4.1. Ranking

For the primary analysis of 6MWT, subjects will be ranked as follows ordered from worst to best:

1. Subjects who died prior to EEOS where time to death is used to rank earlier deaths worse than later deaths,
2. Subjects who are missing EEOS and vital status is unknown at EEOS will be ranked according to time on study drug from worst (shortest time) to best (longest time)
3. Subjects who are missing EEOS because the subject physically cannot perform the test, due to physical incapacity or other reason will be ranked according to time on study drug from worst (shortest time) to best (longest time)
4. Subjects who are missing EEOS and are known to be alive will be ranked according to time on study drug from worst (shortest time) to best (longest time)
5. Completed subject’s values will be ranked from worst (lowest distance) to best (highest distance) performance

Sensitivity analyses of the ranking will be performed by

- a) Only including ranks 1 and 5 above, and for missing reasons besides death, duration on study will be used to rank with shorter duration worse than longer duration
- b) Only including ranks 1, 3, and 5 above, and duration on study will be used to rank subjects who did not die and who are physically able to perform the test with shorter duration worse than longer duration
- c) Imputing subjects who died and who are physically not able to perform the test as zero distance in meters first, then imputing ranks for missing data using ranks 2, 4, and 5 above
- d) Imputing subjects who died or who are physically not able to perform the test (due to physical incapacity, hospitalization, or other reason) as zero distance in meters first, then imputing other missing values as the median of the observed placebo subjects at

the specified visit, then ranking all values from worst (lowest distance) to best (highest distance) performance.

The ranking paradigm with 5 levels and the ranking paradigms a and c above will also be used as sensitivity analyses for the SF-36v2 PCS score key secondary endpoint analyses.

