A plot of the EEOS change from baseline values will be presented. If visual inspection of the data finds the normality assumption is violated, a non-parametric rank analysis of covariance model (ANCOVA) including fixed effects for randomization strata and treatment group, with the ranked baseline value included as a covariate will be used and the Hodges-Lehman estimate of the median treatment difference with associated 95% CI will be presented. A plot of the EEOS change from baseline ranks will be presented. If visual inspection of the ranks finds the normality assumption is violated, the change from baseline at EEOS in SF-36v2 PCS score will be analyzed using a van Elteren test with stratification by randomization strata.

Estimates of least-square (LS) means, standard errors (StdErr), and 95% CIs will be presented by treatment group. In addition, the LS mean difference comparisons between each NEOD001 and placebo, the StdErr of the difference, and 95% CI of the difference will be presented.

Descriptive statistics for SF-36v2 PCS scores, change from baseline, and percent change from baseline will be presented by visit for each treatment group. Mean SF-36v2 PCS scores with associated standard deviation error bars will be plotted by treatment group over time. LS mean change and percent change from baseline in SF-36v2 PCS score with associated StdErr bars will be plotted by treatment group over time. In addition, the cumulative distribution of change from baseline at the EEOS visit will be plotted.

8.8.2. 6MWT Distance to 12 Months of Treatment

The estimand for the 6MWT is the median difference in 6MWT distance change from baseline between treatment groups after 12 months of treatment in all randomized subjects with AL amyloidosis who received any amount of study drug.

The key secondary efficacy analysis will test the following hypotheses:

- H_0 : The distribution of change from baseline in 6MWT distance (meters) after 12 months of treatment is equal between placebo and NEOD001.
- H_1 : The distribution of change from baseline in 6MWT distance (meters) after 12 months of treatment is different between placebo and NEOD001.

For the primary analysis of 6MWT, subjects will be ranked as follows ordered from worst to best:

1. Subjects who died prior to EEOS where time to death is used to rank earlier deaths worse than later deaths

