2. Subjects who are missing EEOS and vital status is unknown at EEOS where duration on study is used to rank shorter duration worse than longer duration will be ranked according to time on study drug from worst (shortest time) to best (longest time)
3. Subjects who are missing EEOS because the subject physically cannot perform the test, due to physical incapacity or other reason where duration on study is used to rank shorter duration worse than longer duration will be ranked according to time on study drug from worst (shortest time) to best (longest time)
4. Subjects who are missing EEOS and are known to be alive where duration on study is used to rank shorter duration worse than longer duration will be ranked according to time on study drug from worst (shortest time) to best (longest time)
5. Completed subject's values will be ranked from worst (lowest distance) to best (highest distance) performance

Sensitivity analyses to assess the effect of missing data are specified in Section 8.2.

Descriptive statistics for 6MWT distance, change from baseline, and percent change from baseline will be presented by visit for each treatment group. The change from baseline at EEOS in 6MWT distance (meters) will be analyzed using a rank ANCOVA model including fixed effects for randomization strata and treatment group, with the ranked baseline value included as a covariate. The Hodges-Lehman estimate of the median treatment difference with associated 95% CI will be presented.

The rank ANCOVA assumes the ranked data are normally distributed and homogenous variance. A plot of the EEOS change from baseline ranks and the baseline ranks will be presented. If visual inspection of the ranks finds the normality assumption is violated, the change from baseline at EEOS in 6MWT distance (meters) will be analyzed using a van Elteren test with stratification by randomization strata.

Only valid assessments 6MWT distance will be included in analysis. Reasons for results being invalid will be presented in a listing and will be finalized prior to database lock. Reasons for results being invalid may include:

- Incorrect course length
- Use of unapproved course
- Unapproved administrator of test
- A site staff member has stopped the stopwatch either inadvertently or incorrectly before the 6 minutes are complete and the subject is still able to walk

In addition, the cumulative distribution of change from baseline at EEOS will be plotted for each treatment group.

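### SAP 8.8.2 does not settle whether 6MWT completers are ranked by distance or by change, and lets an uninformative look at the ranks choose the confirmatory test

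*SAP*

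**What the plan says.** SAP 8.6 makes change from baseline in 6MWT distance the third of four comparisons in a closed fixed sequence at two-sided 0.05.

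SAP 8.8.2 mostly keeps to that variable:
- Estimand: "The estimand for the 6MWT is the median difference in 6MWT distance change from baseline between treatment groups after 12 months of treatment".
- Null hypothesis: "The distribution of change from baseline in 6MWT distance (meters) after 12 months of treatment is equal between placebo and NEOD001".
- Named test: "The change from baseline at EEOS in 6MWT distance (meters) will be analyzed using a rank ANCOVA model", with strata and treatment as fixed effects and ranked baseline as covariate.
- Diagnostic: "A plot of the EEOS change from baseline ranks and the baseline ranks will be presented".

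The ranking list given in the same section for the primary 6MWT analysis departs from it. Item 5, for completers, says their "values will be ranked from worst (lowest distance) to best (highest distance) performance". SAP 8.2.4.1 repeats that item. Sensitivity analysis (d) there imputes distances in meters and ends with "then ranking all values from worst (lowest distance) to best (highest distance) performance".

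On the choice of test, the SAP says "The rank ANCOVA assumes the ranked data are normally distributed and homogenous variance". It continues "If visual inspection of the ranks finds the normality assumption is violated, the change from baseline at EEOS in 6MWT distance (meters" and so on, moving to a stratified van Elteren test. It gives no criterion for the inspection and does not say who inspects or whether that person is blinded. SAP 8.8.1 has the same second-step check on ranks for SF-36v2 PCS.

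Protocol 8.3.2 names van Elteren for 6MWT without condition. SAP Section 10 lists the changed LVEF method but not rank ANCOVA for 6MWT.

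**The concern.** A confirmatory step needs one variable and one test fixed in advance. Here two statisticians could each follow 8.8.2 and rank different variables. The one who follows item 5 would be testing something other than the stated hypothesis.

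The switch of test rests on a property that pooled ranks never have. Read strictly, the named test can never be used. Read loosely, someone picks the test by eye.

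At stake is the step 3 result, and with it whether step 4 (NT-proBNP slope) is formally tested.

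**Working it through.** **1. The two rankings are different.** Subject A goes from 500 m to 450 m (change 450 − 500 = −50). Subject B goes from 200 m to 260 m (change 260 − 200 = +60). By distance A ranks above B (450 > 260). By change B ranks above A (+60 > −50). In the simulations below, the two orderings disagree on 32–41% of completer pairs.

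**2. The normality check on ranks.** Untied pooled ranks are the integers 1 to N, whatever the data. Their excess kurtosis is −(6/5)(N² + 1)/(N² − 1). At N = 130 this is −1.2 × 16901/16899 = −1.2001, the value for a uniform distribution. Two standard checks applied to 1..N disagree:

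| N | Shapiro-Wilk p | Lilliefors p |
|---|---|---|
| 100 | 0.0017 (W = 0.955) | 0.48 |
| 130 | 0.0003 | 0.36 |

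So the outcome depends on how strictly one looks, not on the trial's data. The first PCS check in 8.8.1 is on the change values themselves and does not share this defect.

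**3. Inputs for power.** From the documents: 130 subjects randomized 1:1, four strata, two-sided 0.05. The plan gives no 6MWT power. Its only power figure, 91% for the primary endpoint, reproduces at 65 per arm. With p̄ = 0.3625, SE₀ = √(2 × 0.3625 × 0.6375/65) = 0.0843 and SE₁ = √((0.25 + 0.1744)/65) = 0.0808. Then z = (0.275 − 1.96 × 0.0843)/0.0808 = 1.36, which gives power 91.3%.

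Assumed, because the documents give no values:
- strata proportions 40/30/15/15%;
- baseline mean 350 m, SD 100 m, truncated to 100–600 m; EEOS SD 100 m;
- effect 30 m (the category cut-off in SAP 8.10.2.1, not a design effect);
- baseline-to-EEOS correlation 0.5 to 0.9;
- subjects missing at random in both arms and ranked below completers.

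Tests:
- Rank ANCOVA regresses the outcome rank on treatment, ranked baseline and strata, with a t-test on treatment.
- Van Elteren uses T = Σ w_k[R_1k − n_1k(n_k + 1)/2] with w_k = 1/(n_k + 1), and z = T/√Var(T).

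Simulated power in % (3000–4000 replicates per setting, Monte Carlo error about 1 point):

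| Test, share ranked worst | Ranked by | 0.5 | 0.6 | 0.7 | 0.8 | 0.9 |
|---|---|---|---|---|---|---|
| Rank ANCOVA, 0% | change | 46 | 53 | 63 | 79 | 97 |
| | distance | 46 | 52 | 62 | 76 | 95 |
| Rank ANCOVA, 5% | change | 40 | 44 | 55 | 70 | 91 |
| | distance | 39 | 42 | 49 | 57 | 71 |
| Rank ANCOVA, 10% | change | 30 | 36 | 44 | 57 | 85 |
| | distance | 30 | 34 | 37 | 41 | 52 |
| Rank ANCOVA, 15% | change | 24 | 29 | 36 | 48 | 75 |
| | distance | 25 | 26 | 29 | 31 | 36 |
| Van Elteren, 0% | change | 38 | 45 | 56 | 75 | 96 |
| | distance | 37 | 39 | 40 | 39 | 39 |
| Van Elteren, 15% | change | 22 | 26 | 34 | 46 | 74 |
| | distance | 22 | 22 | 21 | 22 | 23 |

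The largest gaps are 75 − 36 = 39 points for rank ANCOVA and 96 − 39 = 57 for van Elteren. Choosing between the two tests, both on change, moves power by 1–8 points with none missing (46 − 38 = 8; 97 − 96 = 1) and by 1–3 points with 15% ranked worst.

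**4. Differing verdicts.** A second assumed setting used a 40 m effect, 5% dead, 10% otherwise missing and correlation 0.5/0.7/0.85. Ranking by distance and by change gave opposite significance verdicts in 24/31/48% of simulated trials with van Elteren and 13/18/31% with rank ANCOVA. Even where average power is equal, the reading can decide the result.

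**5. Type I error.** Each single test on a single variable gives 4–6%. Taking the smaller p of the two change-based tests would give 6–8%, and of all four readings 9.5–12%. These are upper bounds, because the SAP does not permit choosing on p.

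**The case against.** The strongest reply is that the list is a template: missing subjects go below completers, and completers are ordered low to high on whichever variable is being analysed. SAP 8.8.2 says percent change is handled the same way, 8.10.2.1 applies the method to distance, change and percent change alike, and 8.2.4.1 reuses the five levels for PCS, where distance cannot be meant literally. That probably shows the intent. It does not remove the conflict: item 5 says distance in two sections, and sensitivity analysis (d) imputes meters and ranks by distance.

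The second reply is that the largest losses pair van Elteren with distance, although the fallback sentence speaks of change, and that every input is assumed. This stands as a limit on size. For rank ANCOVA with no missing data the cost is only 0–3 points.

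Third, the visual check read literally leads to the protocol's own valid test, and a by-arm plot or a plot of rank against baseline rank could be informative. The first part is correct, which is why test choice is the lesser issue. On the second, the SAP ties the switch to normality of the ranks and specifies no such plot.

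Finally, levels 2 to 4 in 8.8.2 name both duration on study and time on study drug as the ordering variable. That is a separate defect in the same list and does not weaken this one.

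**Conclusion.** The concern holds and should be fixed. The contradiction over the ranked variable is plain in the text and needs no assumption. Its cost in power does depend on assumptions. It is negligible at correlation 0.5. For van Elteren about half or more of the power is lost at correlation 0.8 and above (36/75 = 48% up to 51/74 = 69%). For rank ANCOVA a loss of that size appears only at 0.9 with 15% ranked worst (39/75 = 52%).

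The rank-normality check is wrong as written, but its consequence is small, because either test on change is valid. The omission from SAP Section 10 is a documentation gap only.

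The primary endpoint is unaffected, and 6MWT is confirmatory only after the primary endpoint and PCS succeed.

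**What to change.** - Reword item 5 in SAP 8.8.2 and 8.2.4.1 so that completers are ranked by change from baseline, largest decrease worst and largest increase best.
- State for sensitivity analyses (c) and (d) in 8.2.4.1 whether imputed distances are converted to change before ranking.
- Delete the rank-normality check in 8.8.2 and the second-step check on ranks in 8.8.1.
- Name one unconditional 6MWT test: either rank ANCOVA on the five-level composite with ranked baseline and randomization strata, or the protocol's stratified van Elteren on change. Keep the other as a sensitivity analysis.
- If rank ANCOVA is kept, list it in SAP Section 10 as a change from protocol 8.3.2.
- In the same edit, settle the ordering variable for levels 2 to 4.

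The cost is SAP wording only, with no new data. It must be done before unblinding, since a later choice could be challenged as data-driven.

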8.8.3. NT-proBNP Slope Through 12 Months of Treatment

The estimand for the NT-proBNP is the difference in slopes between treatment groups over 12 months of treatment in all randomized subjects with AL amyloidosis who received any amount of study drug.

The key secondary efficacy analysis will test the following hypotheses:

- H_0 : The rate of change (i.e., slope) of NT-proBNP over 12 months of treatment is equal between placebo and NEOD001.
- H_1 : The rate of change (i.e., slope) of NT-proBNP over 12 months of treatment is different between placebo and NEOD001.

The primary analysis of NT-proBNP will be performed using a general linear mixed effects model to compare the rate of change (i.e., slope) of NT-proBNP over 12 months of treatment between treatment groups. The model will fit a random intercept and slope for each subject and will include fixed effects for treatment group, time, randomization strata, and treatment group \times time interaction. Time will be expressed in months as a continuous variable and will include all scheduled time points including baseline. An unstructured covariance structure will be used to model the within-subject errors. If the computational algorithm fails to converge, the following structures will be executed: heterogeneous Toeplitz, Toeplitz, heterogeneous First-Order Autoregressive [AR (1)], AR(1), heterogeneous compound symmetry (HCS), and compound symmetry (CS). The covariance structure converging to the best fit, as determined by Akaike's information criterion (AIC), will be used. The Kenward and Roger method will be used to calculate the denominator degrees of freedom for the test of fixed effects. The null hypothesis of no difference in slopes between the treatment groups will be determined by testing the significance of the treatment group by time interaction term.

Estimates of the slope will be presented by treatment group along with corresponding 95% CIs. The estimate of the difference between slopes (NEOD001-Placebo) and the 95% CI of the difference between slopes will also be presented. Appropriate contrasts for pairwise differences in coefficients at time points of interest between NEOD001 and placebo with corresponding 95% CIs will be estimated from the model and tested for significance.

8.9. Additional Secondary Efficacy Analysis

8.9.1. Renal Evaluable Subjects: Renal Best Response

The estimand for renal best response is the difference in renal best response rate between treatment groups through 12 months of treatment in all randomized subjects with AL amyloidosis and renal involvement (Section 8.5) who received any amount of drug.

The secondary efficacy analysis will test the following hypotheses:

- H_0 : The percentage of renal best response through 12 months of treatment is equal between placebo and NEOD001.
- H_1 : The percentage of renal best response through 12 months of treatment is different between placebo and NEOD001.

All visits after the first infusion of study drug up to and through the EEOS visit will be used to evaluate 12 months of treatment. Best renal response will be analyzed in the same manner described in Section 8.7 for the primary efficacy endpoint.

If an assessment qualifies as both response and progression (see Section 2.3.3.1), then assessments will be counted as progression for the primary analysis. A sensitivity analysis will be conducted counting an assessment that qualifies both as response and progression as a response.

8.9.2. Peripheral Neuropathy Evaluable Subjects: NIS-LL Total Score

The estimand for peripheral neurological function is the mean difference in NIS-LL total score change from baseline between treatment groups after 12 months of treatment in all randomized subjects with AL amyloidosis and peripheral neuropathy involvement (Section 8.5) who received any amount of study drug.

The secondary efficacy analysis will test the following hypotheses:

- H_0 : The mean change from baseline in NIS-LL total score after 12 months of treatment is equal between placebo and NEOD001.
- H_1 : The mean change from baseline in NIS-LL total score after 12 months of treatment is different between placebo and NEOD001.

The change from baseline in NIS-LL total score will be analyzed in the same manner described for SF-36v2 PCS score in Section 8.8.1. The EEOS visit will be used to evaluate 12 months of treatment.

If the assumptions of the planned parametric analyses are violated and inhibit the interpretation of the results, appropriate data transformations or non-parametric analyses will be performed in addition to the other planned sensitivity analyses to support the interpretation of the treatment effect.

8.9.3. Hepatic Evaluable Subjects: Hepatic Best Response

The estimand for hepatic best response is the difference in hepatic best response rate between treatment groups through 12 months of treatment in all randomized subjects with AL amyloidosis and hepatic involvement (Section 8.5) who received any amount of drug.

The secondary efficacy analysis will test the following hypotheses:

- H_0 : The percentage of hepatic best response through 12 months of treatment is equal between placebo and NEOD001.
- H_1 : The percentage of hepatic best response through 12 months of treatment is different between placebo and NEOD001.

All visits after the first infusion of study drug up to and through the EEOS visit will be used to evaluate 12 months of treatment. Best hepatic response will be analyzed in the same manner described in Section 8.7 for the primary efficacy endpoint.

8.10. Exploratory Efficacy Analyses

For applicable exploratory efficacy analyses, if the assumptions of the planned parametric analyses are violated and inhibit the interpretation of the results, appropriate data transformations or parametric analyses will be performed in addition to the other planned sensitivity analyses to support the interpretation of the treatment effect.

8.10.1. Cardiac Endpoint Analyses

8.10.1.1. Cardiac Biomarkers: NT-proBNP and Troponin T

NT-proBNP and troponin T results, change from baseline, and percentage change from baseline will be analyzed in the same manner described in Section 8.8.1. In addition, the cumulative distribution of NT-proBNP change from baseline at EEOS will be plotted.

Mean NT-proBNP values with associated standard deviation error bars will be plotted by treatment group over time, including a reference line at 1800 ng/L. LS mean change and percentage change from baseline in NT-proBNP with associated StdErr bars will be presented by treatment group over time.

NT-proBNP best response will be determined for different time intervals, such as through 3, 6, and 9 months of treatment. Best response at each of these and response at each visit will be analyzed in the same manner described in Section 8.7 and Section 8.7.1.

If sufficient mortality data are available, NT-proBNP best response will be evaluated as a potential predictor for the primary endpoint using a Cox regression model with time to the primary endpoint as the outcome, fixed effects for treatment group and NT-proBNP best response over different time intervals, and the treatment group \times NT-proBNP best response interaction. In addition, NT-proBNP change from baseline as a continuous variable may also be evaluated as potential predictors of the primary endpoint. Similar analyses may be conducted for additional time to event endpoints.

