2.3. Study Endpoints

2.3.1. Primary Efficacy Endpoint

The primary efficacy endpoint is cardiac response as defined by N-terminal pro-brain natriuretic peptide (NT-proBNP) best response from baseline through 12 months of treatment. All visits after the first infusion of study drug will be included up to and through the EEOS visit.

NT-proBNP response categories are defined as modified from Table 2 in [Comenzo, 2012](#) ([Appendix 2](#)):

Response	Stable	Progression
Decrease in NT-proBNP from baseline of >30% and >300 ng/L	Assessment was neither Response nor Progression	Increase in NT-proBNP from baseline of >30% and from baseline >300 ng/L

Best response is defined as the most favorable category (response, stable, or progression) across all visits. Subjects will be classified as responders or non-responders. Non-response is defined as either stable or progression.

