8.10.7. Additional Time-to-Event Endpoints

8.10.7.1. Time to All-Cause Mortality (Overall Survival)

Overall survival, time to all-cause mortality, will be calculated in days as the date of death minus the date of first study drug infusion plus 1. Subjects will be censored at their last assessment known to be alive prior to LSLV.

NEOD001 will be compared to placebo using the log rank test stratified by the randomization stratification factors. Kaplan-Meier (KM) estimates of the distribution of the time-to-event will be tabulated and graphed by treatment group. The tabulation will include the KM estimate of the medians, 25th and 75th quartiles, and corresponding 95% CIs, if estimable. The tabular and graphical summaries will include the at-risk counts for every visit. The number and percent of subjects censored and with events will be presented. The hazard ratio and 95% CI will be determined based on a Cox regression model stratified by randomization strata to estimate the magnitude of the effect.

In addition, the frequency of deaths in NEOD001 and placebo will be analyzed in the same manner described in Section 8.7 for the primary efficacy endpoint.

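### The exploratory Cox model in SAP 8.10.1.1 predicts the primary endpoint from itself; if it is run on death instead, it favours responders because response is neither landmarked nor time-updated

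*SAP*

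**What the plan says.** SAP 2.3.1 defines the endpoint: "The primary efficacy endpoint is cardiac response as defined by N-terminal pro-brain natriuretic peptide (NT-proBNP) best response from baseline through 12 months of treatment". Subjects are then classed as responders or non-responders, taking the most favourable category over all visits.

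SAP 8.10.1.1 first sets the intervals: "NT-proBNP best response will be determined for different time intervals, such as through 3, 6, and 9 months of treatment". The next analysis opens with a condition, "If sufficient mortality data are available", and continues: "NT-proBNP best response will be evaluated as a potential predictor for the primary endpoint using a Cox regression model". The model is specified "with time to the primary endpoint as the outcome, fixed effects for treatment group and NT-proBNP best response over different time intervals", plus the treatment-by-response interaction. The same paragraph allows the continuous NT-proBNP change as a predictor, and similar analyses of further time-to-event endpoints.

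Death is a separate exploratory endpoint. Under SAP 8.10.7.1 overall survival "will be calculated in days as the date of death minus the date of first study drug infusion plus 1", and survivors are censored when last known alive before the last subject's last visit.

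**The concern.** There are two faults, one behind the other.

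- **The outcome is misnamed.** The section asks for "time to the primary endpoint as the outcome", but the primary endpoint is a binary classification that is already the predictor. A programmer following the text would either fit a circular model or have to choose the outcome later.
- **The likely intended model is biased.** If the outcome is death, the clock starts at first infusion, while response is settled only at later visits. A subject has to be alive at a visit to be classed as a responder. The time before response is therefore credited to responders although they could not have died in it, and all deaths before a possible response fall on the non-responders. Responders look protected even when response and death are unrelated.

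This model would examine, inside the trial, the link between falling NT-proBNP and lower mortality that Protocol 1.2 and SAP 2.3.2.3 take from published work. A result tilted towards confirming that link would be misleading even as exploratory evidence.

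**Working it through.** **The plan's own figure.** The Cox model has none. The only power figure is for the primary test (SAP 3: 50% vs 22.5%, two-sided 0.05). With 65 per arm and the pooled normal approximation, the mean rate is 0.3625, the null SE is √(2 × 0.3625 × 0.6375 / 65) = 0.0843 and the alternative SE is √((0.25 + 0.1744) / 65) = 0.0808. Then z = (0.275 − 1.96 × 0.0843) / 0.0808 = 1.36, giving 91.3%. At 50 per arm the result is 82.6%. Both stated figures reproduce, and nothing below changes them.

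**Inputs from the documents.** Post-baseline NT-proBNP visits fall every 28 days to Day 308, plus the efficacy end-of-study visit at Day 338 (SAP 4.6, Table 3). Month 3 is Day 56, Month 6 is Day 140 and Month 9 is Day 224. N is up to 130. The time origin is first infusion.

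**Assumptions not in the documents.** Response and death are independent (true hazard ratio 1.0). Annual mortality is 5%, 10% or 20%. The response hazard is constant and reaches 22.5%, 36% or 50% at 12 months. Follow-up either ends at Day 338 or is uniform over 338–730 days. Treatment and interaction terms are omitted.

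**Simulation.** With 400,000 subjects per scenario and best response as a time-fixed covariate, the apparent hazard ratios were:

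| Best response through | Follow-up 338–730 days | Follow-up ends Day 338 |
|---|---|---|
| Month 3 (Day 56) | 0.88–0.92 | 0.79–0.87 |
| Month 6 (Day 140) | 0.79–0.84 | 0.69–0.71 |
| Month 9 (Day 224) | 0.67–0.74 | 0.54–0.60 |
| 12 months (Day 338) | 0.52–0.62 | 0.35–0.42 |

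The bias grows with the response interval, shrinks with longer follow-up and hardly depends on mortality.

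**Hand check.** Let p be the share of responders and *a* the mean day of first response divided by the follow-up time. For low mortality, responders' deaths are reduced by the factor (1 − a) and the non-responders' death rate is inflated by 1 + a·p/(1 − p), so the apparent ratio is about (1 − a) / (1 + a·p/(1 − p)). Take 50% response at 12 months. With a constant per-visit hazard of ln 2/12, the mean response day over the visit schedule is 163.

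- Follow-up 338 days: a = 163/338 = 0.482, ratio = 0.518/1.482 = 0.35.
- Mean follow-up (338 + 730)/2 = 534 days: a = 0.305, ratio = 0.695/1.305 = 0.53.

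Both agree with the table.

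**With the analysis corrected.** In the same scenarios, time-dependent response gives 0.97–1.01. A landmark at the end of the interval gives 0.91–1.03, the spread being simulation error where events are few.

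**False positives at N = 130.** With 40% response and mortality from 5% to 20%, p < 0.05 occurs in at most about 5% of trials for Months 3 and 6, about 4–13% for Month 9 and about 8–36% for 12 months. These rates are less stable than the hazard ratios. The assumed mortality gives only about 6 to 24 deaths by Day 338: 130 × (1 − 0.95^(338/365.25)) = 6.0 and 130 × (1 − 0.80^(338/365.25)) = 24.3. With so few deaths the rate depends on the test used. A second simulation of the 12-month case, which also varied the response rate, ranged from about 1% (5% mortality) to 48% (20% mortality, 50% response).

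**The case against.** **The analysis is minor.** It is exploratory and conditional on mortality data. It lies outside the gatekeeping sequence and does not compare the arms on efficacy. This stands and limits the severity.

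**For the listed intervals the bias is modest.** The SAP names 3, 6 and 9 months as examples. For the first two the false-positive rate stays near or below nominal, mainly because deaths are few. This also stands. A reader might settle on one dramatic figure, such as a hazard ratio of 0.55 with 26% of trials significant, but that applies to 12-month best response at an assumed 15% mortality without the treatment and interaction terms. The SAP's examples do not include 12 months, though they do not exclude it. With the interaction fitted, the response coefficient refers to one arm and rests on fewer deaths, so these percentages do not carry over directly.

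**Fixed effects need not mean fixed in time.** Correct: the term means non-random effects, and a reader should not infer more from it. The bias follows from the absence of any landmark, delayed entry or time-updating.

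**Other text might repair it.** SAP 8.2.2 treats a subject as a non-responder until response occurs, but that is a missing-data rule for responder endpoints and does not define a Cox covariate. SAP 10, on changes to the planned analyses, does not address the point.

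**Surrogacy.** A reader might infer that the model is meant to establish NT-proBNP as a surrogate for survival. The documents do not say so. The SAP speaks only of a potential predictor, and the rationale for the endpoint cites external literature.

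**Conclusion.** The point holds. As written the model is circular: SAP 2.3.1 and 8.10.1.1 make the same variable outcome and predictor. On the likely intended reading, death timed from first infusion, it is biased in favour of responders. That direction follows from the construction and not from the assumed mortality. The size does rest on the assumptions above. The apparent hazard ratio under no association runs from about 0.9 for the shortest listed interval to about 0.7 for the longest with 338–730 days of follow-up, reaches 0.52–0.62 if 12-month response is used, and is further from 1 if follow-up ends at Day 338.

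This is more than missing detail, since following the text gives either a meaningless or a biased result. It is still a fault in one exploratory analysis and gives no ground for doubting the primary Cochran-Mantel-Haenszel test, the fixed-sequence procedure or the 91% power.

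**What to change.** In SAP 8.10.1.1:

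1. Replace the reference to the primary endpoint with all-cause mortality as defined in Section 8.10.7.1.
2. Enter response as a time-dependent covariate that switches on at the visit where it is first met. Alternatively, use a landmark at the end of each response interval: only subjects still alive and followed at that day, response status as of that day, time counted from it.
3. Apply the same rule to the continuous NT-proBNP change and to the additional time-to-event endpoints. Where NT-proBNP progression is itself an event (cardiac progression-free survival, time to cardiac progression), state also that predictor and outcome share measurements, which a landmark does not remove.
4. In SAP 8.2.3.3, correct the wording that treats the primary endpoint as an event that a subject reaches.

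The cost is SAP wording; the data are the same and no sample size changes. The time-dependent version keeps every death. The landmark version drops the deaths before it. With 130 × (1 − (1 − m)^(D/365.25)) for annual mortality m of 5% to 20%, that is about 1–4 deaths at Day 56, 3–11 at Day 140 and 4–17 at Day 224. The loss is small for the early landmarks but a sizeable share of the 6–24 deaths expected by Day 338 for the Month 9 landmark, which favours the time-dependent form if follow-up is short.
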